5.3 Dose modifications / Management of Adverse Reactions

Toxicity will be assessed using the NIH-NCI Common Terminology Criteria for Adverse Events, version 3.0 (CTCAEv3.0, (<http://ctep.cancer.gov/forms/CTCAEv3.pdf>)).

Dose Modification Table:

Dose level	-2	-1	0
RAD001	Off study	5 mg daily	10 mg daily
Letrozole	Off study	2.5 mg daily	2.5 mg daily

Patients will be removed from study for any:

- grade 4 treatment-related toxicity (assuming that appropriate preventive therapy has been given where possible – e.g. antiemetic therapy in case of vomiting, lipid-lowering drug in case of hyperlipidemia), or
- hematologic or non-hematologic toxicity requiring interruption of one or both drugs for > 3 weeks. For detailed recommendations on dose interruption and modification due to suspected toxicity, please refer to the following table.

**Algorithm for interpretation and dose modification
 due to suspected treatment related toxicity:**

Treatment-related toxicity	Actions
Non-hematological toxicity	
Grade 2 (except fatigue, hyperlipidemia, and non-infectious pneumonitis – see Dose Modification Table, page 30)	For first occurrence, interrupt RAD001 (continue letrozole) until recovery to grade ≤ 1 then reintroduce RAD001 (no dose reduction). If the event recurs, interrupt study treatment (Letrozole and RAD001) until recovery to grade ≤ 1 then reintroduce therapy at -1 dose level. If the event recurs a 3 rd time, remove patient from study.
Grade 3 (except hyperlipidemia and non-infectious pneumonitis)	For first occurrence, interrupt study treatment (Letrozole and RAD001) until recovery to grade ≤ 1 . Then reintroduce therapy at -1 dose level. If the event recurs remove from study. For pneumonitis consider the use of a short course of corticosteroids.
Grade 4	Remove from study.

Lipid-lowering drugs

Increased lipid levels are a known adverse effect of treatment with both RAD001 and aromatase inhibitors. In case of hyperlipidemia (\geq grade 1 hypercholesterolemia with or without hypertriglyceridemia), in addition to dietary advice to patients, an HMG-CoA reductase inhibitor such as atorvastatin, pravastatin or fluvastatin may be associated with study treatment.

Hematological toxicity	

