Non-infectious pneumonitis is a class effect of rapamycin derivatives. Cases of non-infectious pneumonitis (including interstitial lung disease) have also been described in patients taking everolimus (see Section 5 Adverse drug reactions). Some of these have been severe and on rare occasions, a fatal outcome was observed.

A diagnosis of non-infectious pneumonitis should be considered in patients presenting with non-specific respiratory signs and symptoms such as hypoxia, pleural effusion, cough or dyspnoea, and in whom infectious, neoplastic and other non-medicinal causes have been excluded by means of appropriate investigations. Patients should be advised to report promptly any new or worsening respiratory symptoms.

Patients who develop radiological changes suggestive of non-infectious pneumonitis and have few or no symptoms may continue everolimus therapy without dose alteration. If symptoms are moderate (Grade 2), consideration should be given to interruption of therapy until symptoms improve. The use of corticosteroids may be indicated. Everolimus may be reintroduced at a reduced dose until recovery to Grade 1 or better.

For cases where symptoms of non-infectious pneumonitis are severe (Grade 3), everolimus therapy should be discontinued and the use of corticosteroids may be indicated until clinical symptoms resolve. Therapy with everolimus may be re-initiated at a reduced dose depending on the individual clinical circumstances.

Worst Grade Pneumonitis	Required Investigations	Management of Pneumonitis	Everolimus Dose Adjustment
Grade 1	CT scans with lung windows and pulmonary function testing including: spirometry, DLCO, and room air O ₂ saturation at rest. Repeat chest x-ray/CT scan every 2 Cycles until return to baseline.	No specific therapy is required	Administer 100% of everolimus dose.
Grade 2	CT scan with lung windows and pulmonary function testing including: spirometry, DLCO, and room air O ₂ saturation at rest. Repeat each subsequent Cycle until return to baseline. Consider bronchoscopy*	Symptomatic only. Prescribe corticosteroids if cough is troublesome.	Reduce everolimus dose until recovery to ≤ Grade 1. Everolimus may also be interrupted if symptoms are troublesome. Patients will be withdrawn from the study if they fail to recover to ≤ Grade 1 within 3 weeks.

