Grade 3	CT scan with lung windows and pulmonary function testing including: spirometry, DLCO, and room air O ₂ saturation at rest; Repeat each subsequent Cycle until return to baseline. Bronchoscopy is recommended*	Prescribe corticosteroids if infective origin is ruled out. Taper as medically indicated.	Hold treatment until recovery to ≤ Grade 1. May restart protocol treatment within 2 weeks at a reduced dose (by one level) if evidence of clinical benefit. Patients will be withdrawn from the study if they fail to recover to ≤ Grade 1 within 2 weeks.
Grade 4	CT scan with lung windows and required pulmonary function testing includes: spirometry, DLCO, and room air O ₂ saturation at rest. Repeat each subsequent Cycle until return to baseline. Bronchoscopy is recommended*.	Prescribe corticosteroids if infective origin is ruled out. Taper as medically indicated.	Discontinue treatment.

*A bronchoscopy with biopsy and/or bronchoalveolar lavage is recommended.

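### Section 5.3.1 gives two instruction sets for grade 2 and grade 3 non-infectious pneumonitis that do not match, and does not say which prevails

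*Combined protocol and SAP*

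**What the plan says.** All references are to the combined protocol and SAP.

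**Grade 2.** The prose of section 5.3.1 reads "If symptoms are moderate (Grade 2), consideration should be given to interruption of therapy until symptoms improve", followed by "Everolimus may be reintroduced at a reduced dose until recovery to Grade 1 or better". The table in the same section reads "Reduce everolimus dose until recovery to ≤ Grade 1" and "Everolimus may also be interrupted if symptoms are troublesome". It then withdraws a patient who has not reached grade 1 or lower in 3 weeks.

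**Grade 3.** The prose reads "everolimus therapy should be discontinued and the use of corticosteroids may be indicated until clinical symptoms resolve". Its next sentence allows re-initiation at a reduced dose, according to the patient's circumstances. The table holds treatment until grade 1 or lower and adds "May restart protocol treatment within 2 weeks at a reduced dose (by one level) if evidence of clinical benefit". It withdraws a patient who has not recovered in 2 weeks.

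**General rules in section 5.3.** The list under the dose-level table removes a patient when toxicity interrupts one or both drugs for more than 3 weeks. The last row of the algorithm sets this at 3 weeks or more. Neither statement exempts pneumonitis. The algorithm's grade 2 and grade 3 non-hematological rows do exempt it, yet the grade 3 row ends with "For pneumonitis consider the use of a short course of corticosteroids".

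**The concern.** Nothing in section 5.3.1 ranks the prose and the table, so an investigator can follow either and be within the protocol. Section 5.3.1 itself reports that some cases under everolimus were severe and, rarely, fatal. Two centers enroll, and each could manage the same event differently.

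There is also a route to the primary analysis. Section 10.1 counts a patient for toxicity alone if she leaves treatment for a reason other than progression before response is established. If one source withdraws her and the other does not, the choice of source can decide whether she counts toward the CR + PR + SD rate.

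**Working it through.** The plan states no figure on this point, so the check sets the sources side by side.

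| Item | Prose, 5.3.1 | Table, 5.3.1 |
|---|---|---|
| Grade 2, first action | Consider interruption; no reduction required if dosing continues | Reduce the dose; interruption optional |
| Grade 2, withdrawal | None of its own | No recovery to grade 1 or lower in 3 weeks |
| Grade 3, first action | Stop everolimus | Hold treatment |
| Grade 3, restart | Reduced dose, by individual circumstances | One level lower, after recovery to grade 1 or lower, within 2 weeks, with evidence of clinical benefit |
| Grade 3, withdrawal | None of its own | No recovery to grade 1 or lower in 2 weeks |

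**Step 1: a grade 2 case.** A patient is still at grade 2 after 3 weeks and dosing was never interrupted. Under the table she is withdrawn. Under the prose she is not. The general limits do not reach her, because they count time off drug, not time unrecovered.

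**Step 2: a grade 3 case.** Assume every clock starts on the day everolimus is stopped; the table does not say when its clock starts. The table's limit is 2 × 7 = 14 days and the general limit is 3 × 7 = 21 days. A patient who first reaches grade 1 on days 15 to 20 may restart under the prose and is inside both forms of the general limit. Under the table she is withdrawn. On day 21 exactly, the two general statements themselves part: one requires more than 3 weeks, the other 3 weeks or more.

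**Step 3: the benefit condition.** The prose has none. The table has one but does not define it. The first scheduled imaging is after cycle 2, at about 8 weeks (section 5.2.6). For an earlier event the plan does not say what evidence would satisfy it.

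**Step 4: does section 5.3 settle it?** No. The grade 2 row sends the reader to the Dose Modification Table on page 30, which lists dose levels only; the contents place 5.3.1 on page 33. The grade 3 row excludes pneumonitis and then advises on it. Corticosteroids at grade 3 thus appear in three strengths: possibly indicated (prose), prescribed once infection is ruled out (table), and to be considered as a short course (5.3 row).

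**Step 5: link to the primary endpoint.** Stable disease must be confirmed at least 8 weeks after it is first met (section 6.3), and the first evaluation is at about 8 weeks. If established means confirmed, the period in which withdrawal could make a patient toxicity-only runs to about 8 + 8 = 16 weeks.

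**The case against.** The strongest reply is that the two sources are close and section 5.3 fills most of the gap. At grade 3 both stop everolimus and both permit a reduced-dose restart, and the prose's open wording can be read as completed by the table's conditions. At grade 2 both speak of a reduced dose until recovery. Interruptions under the prose are already capped at about 3 weeks by the general limits. The corticosteroid remark in section 5.3 is arguably stray text.

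Much of this stands, and it rules out several stronger readings:

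- A reader might infer that a grade 3 event can lead to continued dosing. Neither source allows that; continuation is possible only at grade 2.
- A reader might take the grade 3 prose as permanent discontinuation. The sentence after it allows re-initiation.
- A reader might treat withdrawal as a rival first instruction. It is a later step in the table, conditional on non-recovery.
- A reader might conclude that the prose has no time limit at all. It has none of its own, but the general limits apply to any interruption.
- A reader might size the problem as 0.02 × 42 = 0.84 cases, each worth 1/35 = 2.9 points. The 2% is the threshold for listing grade 3-4 reactions in a renal-cancer trial of everolimus (section 1.4.4.2), not a rate for this regimen. It includes grade 4, which is not in dispute. Only the unknown share of cases in which the sources lead to different outcomes would matter. Section 10 also plans to replace 7 inevaluable patients (35 + 7 = 42), so the denominator is meant to stay at 35.

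The evaluability effect is not settled either. Section 7.1.1 counts a patient with measurable disease who had at least one cycle and was re-evaluated, and section 6.4 schedules end-of-treatment imaging.

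The reply does not remove the two cases in steps 1 and 2. In each, both courses comply with one part of section 5.3.1 and the outcomes are opposite. Reading the table into the prose is reasonable, but the plan does not say to do so.

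**Conclusion.** The point holds as an inconsistency within the protocol. At grade 2 the default action differs, and only the table withdraws a patient who is unrecovered at 3 weeks without interruption. At grade 3 the restart conditions differ, and only the table withdraws at 2 weeks; the time conflict is confined to recovery between 2 and 3 weeks, on the assumption that the clocks start together. The cross-references in section 5.3 do not resolve either difference.

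The effect on efficacy evaluability is possible under section 10.1 but has no computable size, because the documents give no pneumonitis rate for this combination. The case for acting rests on consistent handling, across two centers, of a toxicity that can be fatal. It does not rest on a demonstrated bias in the response rate. No view is taken on which rule is clinically right.

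**What to change.** Reconcile the section 5.3.1 prose, the section 5.3.1 table and the pneumonitis wording in the section 5.3 rows into one instruction per grade. Each should state the action on everolimus, the restart condition and the time limit with its starting point, and should be consistent with a single form of the general interruption limit. If the clinical-benefit condition is kept, say what counts as evidence before the first scheduled scan. Correct the page 30 cross-reference, and place the corticosteroid advice where pneumonitis is actually handled. The sponsor's clinicians decide which rules apply.

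The cost is amendment wording. Sample size, stopping boundaries and assessment schedule are unaffected.

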5.3.2 Management of Hepatitis reactivation

In cancer patients with hepatitis B, whether carriers or in chronic state, use of antivirals during anticancer therapy has been shown to reduce the risk of hepatitis B virus (HBV) reactivation and associated HBV morbidity and mortality (Loomba et al. 2008).

Monitoring and prophylactic treatment for hepatitis B reactivation

Table 3-2 provides details of monitoring and prophylactic therapy according to the baseline results of viral load and serologic markers testing.

Table 3-2 Action to be taken for positive baseline hepatitis B results

Test	Result	Result	Result	Result	Result
HBV-DNA	+	+ or -	-	-	-
HBsAg	+ or -	+	-	-	-
HBs Ab	+ or -	+ or -	+ and no prior HBV vaccination	+ or -	- or + with prior HBV vaccination
HBc Ab	+ or -	+ or -	+ or -	+	-
Recommendation	Prophylaxis treatment should be started 1-2 weeks prior to first dose of study drug Monitor HBV-DNA approximately every 4 weeks		No prophylaxis Monitor HBV-DNA approximately every 4 weeks		No specific action

Antiviral prophylaxis therapy should continue for at least 4 weeks after last dose of study drug.

For patients who have already received study drug prior to the approval of the amendment, the same process should be followed at the patient's next visit. The first HBV-DNA result would be regarded as baseline.

For hepatitis B reactivation, definition and management guidelines, see Table 3-3 Guidelines for management of hepatitis B.

Table 3-3 Guidelines for management of hepatitis B

HBV reactivation (with or without clinical signs and symptoms)*	

For patients with baseline results: Positive HBV-DNA OR positive HBsAg ----- reactivation is defined as: [Increase of 1 log in HBV-DNA relative to baseline HBV-DNA value OR new appearance of measurable HBV-DNA] AND ALT elevation x 5 ULN
	
Treat: Start a second antiviral AND Interrupt study drug administration until resolution: ≤ grade 1 ALT (or baseline ALT, if > grade 1) and ≤ baseline HBV-DNA levels If resolution occurs within ≤ 28 days study drug should be re-started at one dose lower, if available. If the patient is already receiving the lowest dose of study drug according to the protocol, the patient should restart at the same dose after resolution. Both antiviral therapies should continue at least 4 weeks after last dose of study drug. If resolution occurs > 28 days Patients should discontinue study drug but continue both antiviral therapies at least 4 weeks after last dose of study drug.


For patients with baseline results: Negative HBV-DNA and HBsAg AND [Positive HBs Ab (with no prior history of vaccination against HBV), OR positive HBc Ab] ----- reactivation is defined as: New appearance of measurable HBV- DNA
	
Treat : Start first antiviral medication AND Interrupt study drug administration until resolution: ≤ baseline HBV-DNA levels If resolution occurs within ≤ 28 days study drug should be re-started at one dose lower, if available. If the patient is already receiving the lowest dose of study drug according to the protocol, the patient should restart at the same dose after resolution. Antiviral therapy should continue at least 4 weeks after last dose of study drug. If resolution occurs > 28 days Patients should discontinue study drug but continue antiviral therapy at least 4 weeks after last dose of study drug.

* All reactivations of hepatitis B are to be recorded as grade 3 (CTCAE v 3.0 Metabolic Laboratory/Other: Viral Re-activation), unless considered life threatening by the investigator; in which case they should be recorded as grade 4 (CTCAE v 3.0 Metabolic Laboratory/Other: Viral Re-activation). Date of viral reactivation is the date on which **both** DNA and ALT criteria were met (e.g. for a patient who was HBV-DNA positive on 01-JAN-10 and whose ALT reached ≥ 5 × ULN on 01-APR-10, the date of viral reactivation is 01-APR-10).

5.3.3 Monitoring for hepatitis C

The following two categories of patients should be monitored every 4 weeks for HCV reactivation:

- Patients with detectable HCV RNA-PCR test at baseline.
- Patients known to have a history of HCV infection, despite a negative viral load test at baseline (including those that were treated and are considered 'cured')

For definition of hepatitis C reactivation and the management guidelines, see Table 3-4 Guidelines for management of hepatitis C.

Table 3-4 Guidelines for management of hepatitis C

HCV reactivation*	
For patients with baseline results: Detectable HCV-RNA, ----- reactivation is defined as: ALT elevation x 5 ULN	Discontinue study drug
For patients with baseline results: Knowledge of past hepatitis C infection with no detectable HCV-RNA, ----- reactivation is defined as: New appearance of detectable HCV-RNA	Discontinue study drug

* All reactivations of hepatitis C are to be recorded as grade 3 (CTCAE v3.0 Metabolic Laboratory/Other: Viral Re-activation), unless considered life threatening by the investigator; in which case they should be recorded as grade 4 (CTCAE v 3.0 Metabolic Laboratory/Other: Viral Re-activation).

5.3.4 Concomitant therapy

Lipid-lowering drugs

Increased lipid levels are a known adverse effect of treatment with both RAD001 and aromatase inhibitors. In case of hyperlipidemia (\geq grade 1 hypercholesterolemia with or without hypertriglyceridemia), in addition to dietary advice to patients, an HMG-CoA reductase inhibitor such as atorvastatin, pravastatin or fluvastatin may be associated with study treatment.

- It is highly recommended that patients positive HBV-DNA or HBsAg are treated prophylactically with an antiviral for 1-2 weeks prior to receiving study drug (see Section 3.2).
- The antiviral treatment should continue throughout the entire study period and for at least 4 weeks after the last dose of study drug.
- Patients on antiviral prophylaxis treatment or positive HBV antibodies should be tested for HBV-DNA according to study visit schedule.

- Oral contraceptives in preclinical and clinical data have shown everolimus to have CYP3A4 inhibitory activity rather than induction activity, induction of metabolism of contraceptive hormones by everolimus is unlikely. Consequently, administration of everolimus should not reduce the efficacy of oral contraceptives.
- Patients will be provided a list of all drugs/substances to avoid when entered on the study (Appendix E).

5.3.5 INDUCERS & INHIBITORS OF CYP3A4 AND/OR PgP and OTHER RELEVANT DRUG INTERACTIONS

Table 3-5 Inducers/Inhibitors of CYP3A4 and/or PgP

Inhibitors of CYP3A4 and/or PgP
 
Co-administration with strong inhibitors of CYP3A4 (e.g., ketoconazole, itraconazole, ritonavir) or P-glycoprotein (PgP) should be avoided.
 
Co-administration with moderate CYP3A4 inhibitors (e.g., erythromycin, fluconazole) or PgP inhibitors should be used with caution. If patient requires co-administration of moderate CYP3A4 inhibitors or PgP inhibitors, reduce the dose of everolimus to half the currently used dose e.g., 10mg daily would be reduced to 5mg daily. Additional dose reductions to every other day may be required to manage toxicities. If the inhibitor is discontinued the everolimus dose should be returned to the dose used prior to initiation of the moderate CYP3A4/PgP inhibitor.
 
Seville orange, star fruit, grapefruit and their juices affect P450 and PgP activity. Concomitant use should be avoided.

Inducers of CYP3A4 and/or PgP
 
Avoid the use of strong CYP3A4 inducers. If patient requires co-administration of strong CYP3A4 inducers (i.e., phenytoin, carbamazepine, rifampin, rifabutin, phenobarbital, St. John's wort), an increase in the dose of everolimus up to twice the currently used daily dose should be considered, using 5mg increments. Enzyme induction usually occurs within 7-10 days, therefore everolimus dose should be increased by one increment 7 days after the start of the inducer therapy. If no safety concerns are seen within the next 7 days, the dose can be increased again one additional increment up to a maximum of twice the daily dose used prior to initiation of the strong CYP3A4 inducer.
 
This dose adjustment of everolimus is intended to achieve similar AUC to the range observed without inducers. However, there are no clinical data with this dose adjustment in patients receiving strong CYP3A4 inducers. If the strong inducer is discontinued the everolimus dose should be returned to the dose used prior to initiation of the strong CYP3A4/PgP inducer.

Table 3-6
Clinically relevant drug interactions: substrates, inducers, and inhibitors of isoenzyme CYP3A

SUBSTRATES	
Antibiotics: Clarithromycin, erythromycin, telithromycin	Calcium channel blockers: Amlodipine, diltiazem, felodipine, lercanidipine, nifedipine, nisoldipine, nitrendipine, verapamil
Anti-arrhythmics: Quinidine	HMG CoA reductase inhibitors: Cerivastatin, lovastatin, simvastatin
Benzodiazepines: Alprazolam, diazepam, midazolam, triazolam	Steroid 6beta-OH: estradiol, hydrocortisone, progesterone, testosterone
Immune modulators: Cyclosporine, tacrolimus (FK506)	Miscellaneous: Alfentanil, aprepitant, aripirazole, buspirone, cafergot, caffeine, cilostazol, cocaine, codeine-N-demethylation, dapsone, dexamethasone, dextromethorphan, docetaxel, domperidone, eplerenone, fentanyl, finasteride, Gleeevec/imatinib, haloperidol, irinotecan, LAAM, lidocaine, methadone, nateglinide, ondansetron, pimoziide, propranolol, quetiapine, quinine, risperidone, salmeterol, sildenafil, sirolimus, sorafenib, sunitinib, tamoxifen, taxol, terfenadine, torisel, trazodone, vincristine, zaleplon, ziprasidone, zolpidem
HIV Antivirals: Indinavir, nelfinavir, ritonavir, saquinavir	
Prokinetic: Cisapride	
Antihistamines: Astemizole, chlorpheniramine, terfenadine	
INDUCERS	
Barbiturates, carbamazepine, glucocorticoids, modafinil, oxcarbazepine, phenobarbital, phenytoin, pioglitazone, rifabutin, rifampin, St. John's wort, troglitazone, efavirenz, nevirapine	
INHIBITORS	
Strong inhibitors: indinavir, nelfinavir, ritonavir, clarithromycin, itraconazole, ketoconazole, nefazodone, saquinavir, telithromycin, Posaconazole (Krishna et al, 2009)	
Moderate inhibitors: aprepitant, diltiazem, erythromycin, fluconazole, grapefruit juice, verapamil,	
Weak inhibitors: Cimetidine, Seville orange (Malhotra et al, 2001)	
Unclassified as per the Indiana University DDI listing: Ciprofloxacin, delaviridine, troleandomycin, mibefradil, amiodarone, chloramphenicol, diethyldithiocarbamate, fluvoxamine, starfruit, gestodene, imatinib, mifepristone, norfloxacin, norfluoxetine, voriconazole*,	

Based on <http://medicine.iupui.edu/clinpharm/ddis/table.asp> as of December 01, 2009

* Voriconazole (unclassified as per the Indiana University DDI table)

Strong inhibitor according to the following reference:
 (<http://www.nature.com/clpt/journal/v80/n5/pdf/clpt2006438a.pdf>)

Table 3-7 Clinically relevant drug interactions mediated by PgP

PgP Substrates	PgP Inhibitors in vivo	PgP Inducers
digoxin, fexofenadine, indinavir, vincristine, colchicine, topotecan, paclitaxel	amiodarone, azithromycin, captopril, carvedilol, clarithromycin, conivaptan, cyclosporine, diltiazem, elacridar, erythromycin, felodipine, (GF120918), itraconazole, ketoconazole, lopinavir, (LY335979), mibefradil, nifedipine, nitrendipine, (PSC833), quinidine, ranolazine, ritonavir, talinolol, valsopodar, verapamil	rifampin, St John's wort

- Seville orange, star fruit, grapefruit and their juices affect P450 and PgP activity. Concomitant use should be avoided
- No chronic treatment with systemic steroids (at a dose equivalent of greater than 20 mg prednisone per day) or other immunosuppressive agents. Topical or inhaled corticosteroids are allowed.
- The use of live vaccines and close contact with those who have received live vaccines should be avoided during treatment with everolimus. Examples of live vaccines include intranasal influenza, measles, mumps, rubella, oral polio, BCG, yellow fever, varicella and TY21a typhoid vaccines.

Oral anticoagulants such as warfarin are CYP2C9 substrates and, as such, no interaction with everolimus is expected. However, drug-drug interaction studies between macrolide antibiotics and warfarin have produced mixed outcomes and the disparity in these findings has led to the conclusion that multiple factors may alter the clearance of warfarin. The coadministration of everolimus and oral anticoagulants is possible but should be subject to verification of coagulation (INR) once steady state is reached (after one week's treatment).

Examples are provided in Table 3-5 (CYP3A4 inhibitors/inducers) and Table 3-6 (Drug interactions mediated by P-glycoprotein). A comprehensive list of cytochrome P450 isoenzymes and CYP3A4 inhibitors, inducers, and substrates can be found at <http://medicine.iupui.edu/flockhart>.

Patients will be provided a list of all drugs/substances to avoid when entered on the study (Appendix E).

